Transvenous ICD and S-ICD systems have traditionally used acute VF conversion testing at the time of system implantation to demonstrate successful VF conversion at an energy level lower than the maximum energy of the pulse generator to allow for a safety margin. ICD safety margins have typically been set ~10 J. In the US S-ICD Pre-market Clinical Study (G090013, commenced 11Dec09), a 15 J safety margin was tested. Thus, acute VF conversion efficacy at 65 J is typically tested during an S-ICD implant. If patients could be converted at energies lower than 65 J, they could potentially receive a smaller, lower energy S-ICD pulse generator. Engineering analysis suggests that a 60 J S-ICD pulse generator could be close to 40 cc in size, which is a substantial reduction compared to 59 cc in an 80 J device.

[figure not shown]
Data collected from an early S-ICD study of 49 subjects showed that the S-ICD system had mean DFT of $\sim 37 \pm 20$ J, and that 38 out of 49 subjects had at least one successful conversion at 50 J or lower¹. Data from two other studies showed the S-ICD system converted VF at energies less than or equal to 50 J in 12 out of 16 subjects with hypertrophic cardiomyopathy² and 11 out of 15 subjects in a subset of the US S-ICD Post-Approval Study (P110042, commenced 28Sep12 as conditions of approval). Thus, while small in number,

the available data suggest that between 70% and 80% of current S-ICD recipients might already meet defibrillation requirements to allow the use of a 60 J pulse generator. Improvements to the S-ICD electrode system that reduced defibrillation energy requirements would increase the percentage of subjects able to receive a smaller, lower energy S-ICD system.

[figure not shown]
4.2. *Bench Test, Computer Modeling, and Pre-clinical Study Results*

A large rectangular area of the page is completely blacked out, indicating that the content has been redacted. This redaction covers the majority of the page below the section header, from approximately y=285 to y=685.

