10.3. Subject Status and Classification

The status of study subjects will be classified as follows:

Enrolled: a subject who has signed and dated the informed consent form

Intent: a subject who signs the informed consent form but does not initiate any part of the S-ICD implant procedure. These include subjects who were found ineligible after consent but prior to S-ICD implant. A withdrawal form will be submitted and the subject is exited from the study and will not be counted towards enrollment ceiling.

Attempt: a subject who has any part of the S-ICD implant procedure started.

Partial Treatment: a subject who has the Investigational S-ICD Y-Adapter connected to the S-ICD pulse generator and the first electrode.

Treatment: a subject who initiates the investigational testing in the 2-electrode configuration (Parallel and 90°) Enrollment Controls

Study sites will be allowed to enroll until the enrollment ceiling of 42 subjects.

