12.1. Study Data

12.1.1. Primary Data and Secondary Data

Primary Data

1. Safety: All device- and procedure-related adverse events through 90 days post-implant procedure.
2. Effectiveness: defibrillation threshold (DFT) of the two-electrode shock configuration - two left-parasternal electrodes to the left lateral PG.

Secondary Data

1. Shock impedance of the electrode conversion tests using both the single electrode (at 65 J) and the 2-electrode configurations (Parallel and 90°).
2. Percentage of defibrillation success of VF conversion at each of the tested energy level

Hypotheses

This is an early-stage feasibility study. There is no formal hypothesis due to study not being powered for its sample size and no control group for comparison. This study seeks to characterize the performance of the new electrode shock configuration by collecting defibrillation conversion and shock impedance data.

Sample Size

This is an early-stage feasibility study and there is no formal sample size calculation. It is estimated that 20 subjects with complete testing, within an electrode configuration, will allow for a reasonable confidence in assessing defibrillation performance. For example, if 19 out of 20 subjects are successfully converted at 50 J (95% success) the resulting 95% confidence interval will be 75.13% to 99.87% using exact test, which is considered acceptable for this early feasibility assessment.

Since some enrolled subjects may not start and/or complete testing due to a variety of reasons, including exceeding the protocol-required safety criteria per Sections 11.4.2 and 11.4.3, and since a protocol revisions was made to add testing of a 2nd 2-electrode configuration (90° configuration), the study will enroll up to 42 subjects so that 30 complete datasets can be expected.

Statistical Methods

This is an early-stage feasibility study to assess performance of the new electrode shock configurations. No specific statistical tests will be performed. Descriptive statistics will be provided as follows,

- Subject demographic and medical history data will be reported as raw numbers and percentage for categorical variables and mean ± standard deviation for continuous variables.
- DFTs and shock impedances will be reported as mean ± standard deviation.
- Defibrillation success at a given energy level (eg 50 J, etc.) will be reported as a percentage and 95% confidence interval.

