12.2. General Statistical Methods

12.2.1. Analysis Sets

Primary Safety analyses will include all Attempt, Partial Treatment, and Treatment subjects, as defined in Section 10.3.

Primary Effectiveness analyses will include all Treatment subjects.

Secondary Effectiveness analyses of one-electrode shock data will include both Partial Treatment and Treatment subjects. Secondary Effectiveness analyses of 2-electrode configuration (Parallel and 90°) shock data will include Treatment subjects.

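### Must Section 12.1.1 spell out the denominator for success at each energy, and the DFT of a subject whom no shock converts?

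*Combined protocol and SAP*

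**What the plan says.** Section 12.1.1 names the secondary measure as "Percentage of defibrillation success of VF conversion at each of the tested energy level". Its Statistical Methods text adds: "Defibrillation success at a given energy level (eg 50 J, etc.) will be reported as a percentage and 95% confidence interval". On the primary effectiveness measure it says only: "DFTs and shock impedances will be reported as mean ± standard deviation". The Sample Size text supports 20 completers per configuration with an example, "if 19 out of 20 subjects are successfully converted at 50 J (95% success"), and an exact 95% interval of 75.13% to 99.87%.

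Section 12.2.1 sets the populations: "Primary Effectiveness analyses will include all Treatment subjects", and "Secondary Effectiveness analyses of 2-electrode configuration (Parallel and 90°) shock data will include Treatment subjects". Section 10.3 defines a Treatment subject as "a subject who initiates the investigational testing in the 2-electrode configuration", so completing the testing is not required.

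Section 11.4 expects two inductions per configuration and refers to Figure 11-1 for the energy steps. The Revision History (revision C) gives a first energy of 30 J, where earlier subjects started at 50 J. Section 27.2 describes DFT testing as step-wise. Figure 11-1 is not reproduced, and most of 11.4.1 to 11.4.5 is redacted.

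**The concern.** In a step-wise sequence the second energy usually depends on the first result. If a subject who converts at 30 J is never shocked at 40 or 50 J, those shocked at the higher energy are only the 30 J failures. Success among them understates what the configuration can do, and the understatement grows as the configuration improves, because fewer and harder cases remain. Dividing by all Treatment subjects without carrying conversions upward is worse still at the higher step. Section 4.1 words its background figure differently: "38 out of 49 subjects had at least one successful conversion at 50 J or lower".

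The DFT mean has a related difficulty. A Treatment subject whom no shock converts has no lowest successful energy, and Section 12 gives no value or exclusion rule. It is also silent on whether the ten datasets from the earlier 50 J-start sequence share tables with the later ones.

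The study plans no tests, so these percentages and means are its effectiveness result. Several readings invite a choice after the data are seen.

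**Working it through.** **1. The plan's figure.** Clopper-Pearson for 19/20: lower limit Beta(0.025; 19, 2) = 75.13%, upper limit Beta(0.975; 20, 1) = 99.87%. This matches Section 12.1.1. Wilson would give 76.39% to 99.11%, so the exact method was used as stated.

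**2. What the denominator does.** Take the plan's 19 conversions in 20. Assume 50 J is given only to 30 J failures, and let m subjects convert at 30 J. Three counts are possible at 50 J:

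- at or below 50 J: 19/20
- among those shocked at 50 J: (19 − m)/(20 − m)
- over all 20, nothing carried upward: (19 − m)/20

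| m | At or below | Among those shocked | Over all 20 |
|---|---|---|---|
| 10 | 95% (75.1–99.9) | 9/10 = 90% (55.5–99.7) | 9/20 = 45% |
| 15 | 95% (75.1–99.9) | 4/5 = 80% (28.4–99.5) | 4/20 = 20% (5.7–43.7) |
| 18 | 95% (75.1–99.9) | 1/2 = 50% (1.3–98.7) | 1/20 = 5% |

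The arithmetic of the concern is right under that assumed sequence.

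**3. Which count the plan's example fits.** A denominator of 20 at 50 J arises in two ways: every subject is shocked at 50 J, or lower-energy conversions count upward. The example may have been written for the 50 J start, where the first holds. With a 30 J start only the second gives it. The stated interval is correct either way. The 4/5 and 4/20 readings fit neither the example's denominator nor its result.

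**4. Subjects with no successful shock.** Assume 20 subjects: ten with a DFT of 20 J, six of 30 J, three of 40 J, one with no success. Excluding the last: (200 + 180 + 120)/19 = 26.3 J, SD 7.6. Setting that subject to 80 J: 580/20 = 29.0 J, SD 14.1. One subject moves the mean by 2.7 J and nearly doubles the SD.

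How often this arises depends on a DFT distribution the documents do not give for two electrodes. Take a lognormal DFT, a sharp threshold, a top step of 40 J, and entry only if DFT ≤ 65 J:

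- Mean 25, SD 13: P(DFT ≤ 40) = 0.886/0.986 = 0.899. At least one non-converter in 20: 1 − 0.899^20 = 88%.
- Mean 20, SD 8: log-scale variance ln(1 + 0.4²) = 0.148, log-scale mean ln 20 − 0.074 = 2.92. P(DFT ≤ 40) = 0.9768/0.9994 = 0.977. At least one in 20: 1 − 0.977^20 = 37%.

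The revision C log says all subjects so far converted at 40 J or lower. If that means the ten complete datasets, its probability is 0.899^10 = 34% in the first case and 0.977^10 = 80% in the second. The lower distribution fits better, and there non-converters are fewer.

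**5. What depends on these summaries.** Section 12.3.1 has two futility triggers: a mean impedance reduction below 10%, and more than three subjects failing 40 J shocks. The first uses no conversion data. The second is a count of subjects, so no denominator enters. Section 12.1.1 plans no tests.

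**6. Whether the data allow the right count later.** Table 11-2 requires an episode and induction report for all shocked episodes, so each shock's result is documented. Any of the three counts, and the number without a success, can be produced at analysis.

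**The case for a change.** The strongest case for a change is that the silence is in unredacted text, that the same data can give 95%, 80% or 20%, and that fixing the count in advance costs a sentence. The DFT is the primary effectiveness measure, and Section 12.2.1 admits subjects who merely start testing. Even if Section 11.4 holds a rule for assigning the DFT, Section 12 does not refer to it.

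The silence stands, and so does the arithmetic. Three things weaken the inference to a change. First, the problem exists only if the second energy depends on the first and no rule appears in Figure 11-1 or 11.4.1 to 11.4.5; redacted or unshown text cannot be counted as absent. No current, visible text says that 50 J is still a step; it appears in Section 12.1.1 only as an example. Second, larger estimates of harm need assumed DFT distributions and an assumed energy sequence. Third, the Section 4.1 figure is one-electrode background, and the plan states that it makes no comparison, so a mismatch with it breaks nothing.

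Nor is the at-or-below count exact. It assumes that a subject converting at a lower energy would convert at a higher one. In simulations with a variable response it overstated success at 40 J by up to about 6 points. On the ten earlier datasets, the revision log already separates them from the twenty needed under the new procedure.

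**Conclusion.** Section 12.1.1 leaves detail out, but no change to the plan is needed. Anyone summarising step-wise DFT data would be expected to count conversion at or below each energy among subjects tested in that configuration, give the number with no successful shock beside the mean, and keep the 50 J-start datasets apart. The plan's 19/20 example agrees with that count, and its interval is correct. The less sensible readings could move the 50 J figure from 95% to 80% or 20% when 15 of 20 convert at 30 J, and one non-converter could move the mean DFT by about 3 J. These sizes rest on an assumed sequence and assumed counts. In a descriptive pilot with no test, and no stopping trigger tied to these percentages, the report can settle the matter by stating its denominators. The conclusion assumes that shock-level results are kept as Table 11-2 requires. It would be weaker if Figure 11-1 and Section 11.4 held no DFT rule and the report gave percentages without denominators.

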12.2. General Statistical Methods

12.2.1. Analysis Sets

Primary Safety analyses will include all Attempt, Partial Treatment, and Treatment subjects, as defined in Section 10.3.

Primary Effectiveness analyses will include all Treatment subjects.

Secondary Effectiveness analyses of one-electrode shock data will include both Partial Treatment and Treatment subjects. Secondary Effectiveness analyses of 2-electrode configuration (Parallel and 90°) shock data will include Treatment subjects.

12.2.2. Number of Subjects per Investigative Site

It is expected that 42 subjects will be enrolled in up to 10 investigative sites.

12.3. *Data Analyses*

12.3.1. *Interim Analyses*

Boston Scientific will monitor the data and perform ongoing analyses on test procedures, and to identify possible safety or futility concerns. For a small early-stage feasibility study such interim analysis cannot be statistically planned or derived. However, the following effectiveness futility triggers are being established and a test configuration may be dropped, or the study will end if these criteria are met.

- <10% reduction in mean shock impedance (after a minimum of 10 subjects enrolled)
- >3 subjects that fail conversion success with 40 J shocks (4 subjects need to fail)

12.3.2. *Changes to Planned Analyses*

Changes from the planned statistical methods outlined in this protocol will be documented in the clinical study report along with a reason for the deviation.

13. *Data Management*

13.1. *Data Collection, Processing, and Review*

Subject data will be recorded on the Technical Source Forms (TSF) and paper case report forms (CRFs) provided by Boston Scientific, and on source documentation. The CRF data shall be derived from and consistent with the source documents and TSFs. Any discrepancies must be explained in writing. Per Good Clinical Practice (GCP), any change or correction made to the original clinical data will be initialed, dated, and explained, if necessary, and shall not obscure the original entry. A written audit trail shall be maintained which will be made available for review by Boston Scientific.

The TSFs are intended to be used to document procedure data during the S-ICD implant where source documentation is not available, and are to be completed by trained, qualified and investigator-authorized staff or Boston Scientific representative. The investigator and the Boston Scientific representative (if present to document the procedure data) will both sign the TSFs to confirm that the forms are a true source of procedure data.

The Principal Investigator will provide their signature on the appropriate source documents, TSFs, and CRFs in compliance with local regulations. A copy of the paper CRFs must be submitted to Boston Scientific. Changes to data previously submitted to the sponsor require a new signature by the Investigator or his/her designee to acknowledge and approve the changes.

Visual review of source documents, TSFs, and CRFs will be performed to identify possible data discrepancies. Manual queries will be created and issued to the site for appropriate response. Site staff will be responsible for resolving all queries.

All access to the clinical database will be changed to “Read only” after all data is either “Hard Locked” or “Entry Locked”. Once acceptance of the final report or finalization of publications (as applicable) is received, final database storage and archiving activities will be completed.

13.2. *Data Retention*

The Principal Investigator or his/her designee or Investigational site will maintain, at the investigative site, all essential study documents and source documentation that support the data collected on the study subjects in compliance with ICH/GCP (International Conference on Harmonization/Good Clinical Practice) guidelines. Documents must be retained until at least 2 years have elapsed since the formal discontinuation of the clinical investigation of the product or until they are no longer needed to support regulatory applications by the study sponsor. These documents will be retained for a longer period of time by agreement with Boston Scientific or in compliance with other country/regional/local regulations.

The Principal Investigator or his/her designee will take measures to ensure that these essential documents are not accidentally damaged or destroyed. If for any reason the Principal Investigator or his/her designee withdraws responsibility for maintaining these essential documents, custody must be transferred to an individual who will assume responsibility and Boston Scientific must receive written notification of this custodial change. Sites are required to inform Boston Scientific in writing where paper or electronic files are maintained in case files are stored off site and are not readily available.

14. Amendments

If there are any changes to the study that affect the rights, safety or welfare of the subject or the scientific integrity of the data, an amendment to this Clinical Investigation Plan is required. Appropriate approvals (e.g., EC/CA) of the revised Clinical Investigation Plan must be obtained prior to implementation.

15. Deviations

An Investigator must not make any changes or deviate from this protocol, except to protect the life and physical well-being of a subject in an emergency. An investigator shall notify the sponsor and the reviewing EC, and the regulatory authority, if applicable of any deviation from the investigational plan to protect the life or physical well-being of a subject in an emergency, and those deviations which affect the scientific integrity of the clinical investigation. Such notice shall be given as soon as possible, but no later than 5 working

days after the emergency occurred, or per prevailing local requirements, if sooner than 5 working days.

All deviations from the investigational plan, with the reason for the deviation and the date of occurrence, must be documented and reported to the sponsor using paper CRF. Sites may also be required to report deviations to the EC and the regulatory authority, per national guidelines and government regulations.

Deviations will be reviewed and evaluated on an ongoing basis and, as necessary, appropriate corrective and preventive actions (including EC notification, Regulatory authority notification, site re-training, or site discontinuation/termination) will be put into place by the sponsor.

The sponsor will not approve protocol waivers.

16. Device/Accountability

The investigational devices shall be securely maintained, controlled, and used only in this clinical study. The investigational device inventory log will be used to track device usage during the study. The Investigational S-ICD Y-Adapter is considered an investigational device in this study.

For the Y-Adapters labelled as investigational, the principal investigator or an authorized designee shall do the following:

- Securely maintain and control access to these items to ensure they are used only in this clinical study and only per the protocol.
- Ensure the storage environment for these items is appropriate for maintaining conditions per the items' labeling (e.g. temperature, humidity, etc., as applicable).
- Return used Y-Adapters after use and return unused or expired Y-Adapters at the end of the study or upon Sponsor request. .

The sponsor shall keep records to document the physical location of all investigational devices from shipment of investigational devices from Boston Scientific or designated facility to the investigation sites until return.

Records shall be kept by the Principal Investigator or his/her designee to document the physical location and conditions of storage of all investigational devices.

- Maintain records of the physical location and conditions of storage of items labelled as investigational.

The principal investigator or an authorized designee shall keep records documenting the receipt, use, and return of the investigational devices, which shall include the following:

- Maintain accurate and timely Device Accountability Records, providing copies to Sponsor upon request. Such records shall include the following content, at minimum:
 - Name of person who received, used, returned or disposed of each item
 - Date of receipt
 - Identification and quantity of each item (examples of identification: batch number, serial number or unique code)
 - Expiry date for each item (or batch of items), as applicable
 - Date or dates of use
 - Subject identification
 - Date on which the item was returned /explanted from subject, if applicable
 - Date of return (and number) of unused, expired, no longer needed or malfunctioning item, as applicable

Date and documentation of item disposal, as directed by sponsor, if applicable.

Written procedures may be required by national regulations.

The sponsor may provide commercially approved devices upon logistics and preferences of the individual study sites. All shipment, disposition and return of such devices should be tracked and unused devices should be returned to the sponsor.

17. Compliance

17.1. Statement of Compliance

This clinical investigation is financed by the study sponsor. Before the investigational site can be “Authorized to Enroll,” the investigational site must enter into a Clinical Study Agreement with the sponsor that details the financing of the study as well as the rights and obligations of the investigational site and the investigator.

This study will be conducted in accordance with the European Medical Device Regulation, ISO14155 Clinical Investigation of Medical Devices for Human Subjects – Good Clinical Practice, the relevant parts of the ICH Guidelines for Good Clinical Practices, ethical principles that have their origins in the Declaration of Helsinki, and pertinent country laws and regulations. The study shall not begin until the required approval/favorable opinion from the EC and regulatory authority has been obtained. Any additional requirements imposed by the EC or regulatory authority shall be followed, if appropriate. An Investigator Brochure is created to support the study.

17.2. *Investigator Responsibilities*

The Principal Investigator of an investigational site is responsible for ensuring that the study is conducted in accordance with the Clinical Study Agreement, the clinical investigation plan, ISO 14155, ethical principles that have their origins in the Declaration of Helsinki, any conditions of approval imposed by the reviewing EC, and prevailing local and/or country laws and/or regulations, whichever affords the greater protection to the subject.

The Principal Investigator's responsibilities include, but are not limited to, the following.

- Prior to beginning the study, sign the Clinical Study Agreement and comply with the Investigator responsibilities as described in such Agreement.
- Prior to beginning the study, sign the Investigator Brochure Signature Page and Protocol Signature page documenting his/her agreement to conduct the study in accordance with the protocol.
- Provide his/her qualifications and experience to assume responsibility for the proper conduct of the study and that of key members of the site team through up-to-date curriculum vitae or other relevant documentation and disclose potential conflicts of interest, including financial, that may interfere with the conduct of the clinical study or interpretation of results.
- Make no changes in or deviate from this protocol, except to protect the life and physical well-being of a subject in an emergency; document and explain any deviation from the approved protocol that occurred during the course of the clinical investigation.
- Create and maintain source documents throughout the clinical study and ensure their availability with direct access during monitoring visits or audits; ensure that all clinical-investigation-related records are retained per requirements.
- Ensure the accuracy, completeness, legibility, and timeliness of the data reported to the sponsor in the CRFs and in all required reports.
- Record, report, and assess (seriousness and relationship to the device/procedure) every adverse event as applicable per the protocol and observed device deficiency.
- Report to sponsor, per the protocol requirements, all reportable events.
- Report to the EC and regulatory authorities any SAEs and device deficiencies that could have led to a SADE and potential/USADE, if required by the national regulations or this protocol or by the EC, and supply Boston Scientific with any additional requested information related to the safety reporting of a particular event.
- Maintain the device accountability records and control of the device, ensuring that the investigational device is used only by authorized/designated users and in accordance with this protocol and instructions for use.

- Allow the sponsor to perform monitoring and auditing activities, and be accessible to the clinical research monitor or auditor and respond to questions during monitoring visits or audit(s).
- Allow and support regulatory authorities and the EC when performing auditing activities.
- Ensure that informed consent is obtained in accordance with applicable laws, this protocol and local EC requirements.
- Provide adequate medical care to a subject during and after a subject's participation in a clinical study in the case of adverse events, as described in the Informed Consent Form (ICF).
- Inform the subject of the nature and possible cause of any adverse events experienced.
- Inform the subject of any new significant findings occurring during the clinical investigation, including the need for additional medical care that may be required.
- Provide the subject with well-defined procedures for possible emergency situations related to the clinical study, and make the necessary arrangements for emergency treatment.
- Ensure that clinical medical records are clearly marked to indicate that the subject is enrolled in this clinical study.
- Ensure that, if appropriate, subjects enrolled in the clinical investigation are provided with some means of showing their participation in the clinical investigation, together with identification and compliance information for concomitant treatment measures (contact address and telephone numbers shall be provided).
- Inform, with the subject's approval or when required by national regulations, the subject's personal physician about the subject's participation in the clinical investigation.
- Make all reasonable efforts to ascertain the reason(s) for a subject's premature withdrawal from clinical investigation while fully respecting the subject's rights.
- Ensure that an adequate investigation site team and facilities exist and are maintained and documented during the clinical investigation.
- Ensure that maintenance and calibration of the equipment relevant for the assessment of the clinical investigation is appropriately performed and documented, where applicable.

All investigators will provide their qualifications and experience to assume responsibility for their delegated tasks through up-to-date curriculum vitae or other relevant documentation and disclose potential conflicts of interest, including financial, that may interfere with the conduct of the clinical study or interpretation of results.

